## **1.0 BACKGROUND & RATIONALE**

Emotional distress in parents and their young child (ages 3-8) with cancer during acute treatment is a prevalent, persistent problem associated with physical symptom distress and diminished quality of life and family function. In the longer term, this acute emotional distress is related to traumatic stress symptoms after treatment ends. As many as 58% of parents and 40% of childhood cancer survivors later report traumatic stress symptoms in the moderate to severe range. These young children and parents require palliative care interventions to manage acute treatment distress and prevent secondary psychosocial morbidity, yet a recent systematic review revealed a glaring absence of empirically validated interventions for this age group.

Music therapy, one of the most frequently used arts-based therapies, has become standard palliative care in many pediatric and adult hospitals; however, few studies have examined mechanisms by which music therapy works. Music-based play is a pervasive, spontaneous, and normal aspect of family life that structures and supports meaningful interactions, and is a primary way young children cope with traumatic experiences.

Based on [name]'s music therapy theoretical framework, we developed and tested the Active Music Engagement (AME) intervention, establishing it as a feasible/acceptable intervention that reduces emotional distress in young children hospitalized for cancer treatment. The music therapist-led AME uses music-based play and parent education/support (music play resource kit; tip sheets). The AME builds on existing skills, minimizing the burden of learning new skills during a stressful time when learning can be less efficient. As parents witness intervention benefits for their child and learn how to use normalizing play activities to help manage their child's distress, traumatic reactions to and distressing memories of hospitalization may be minimized for both children and parents. The AME is particularly viable because it is easy to implement and teaches parents/children how to therapeutically use a familiar activity to manage distress.

As a palliative care intervention, the AME was developed to help manage distress and offer psychosocial support during acute cancer treatment. Three preliminary Active Music Engagement studies were conducted by our research team. **Study 1** was a descriptive study conducted to measure the presence/absence of contextual support (i.e., structure, autonomy support, relationship support) in the environment and levels of child engagement across three conditions (usual care, AME, and audio-storybooks). Findings indicated that the AME intervention: 1) was theoretically aligned with [name]'s Contextual Support Model for Music Therapy (CSM-MT), and 2) engaged children significantly more than usual care or attention control conditions.

**Study 2** was a multi-site, non-randomized (sequential assignment) study that established feasibility/acceptability of a single-session, therapist-led AME intervention and audio-storybooks as an attention control condition. In this study we examined two attention control conditions (music listening and audio-storybooks). Music listening did not demonstrate any significant behavioral benefits and was not well accepted by parents. In contrast, the audio-storybooks condition was acceptable to parents but did not demonstrate any significant behavioral benefits, validating it as the best control condition for our current study. In addition, children randomized to the AME intervention demonstrated significantly more engagement behaviors than children in the control conditions (i.e., the proximal mediator proposed in this trial).

**Study 3** was a randomized pilot study that examined feasibility, acceptability, and preliminary efficacy of a parent implemented AME. In this study we translated the AME into a parent-led intervention and added parent instruction/coaching. Findings indicated the intervention and design were feasible, highly acceptable, demonstrated significantly more child engagement and parent child interaction behaviors, and produced positive outcomes for children. However, although parents were able to deliver the intervention they expressed: 1) preference for more therapist involvement/support during

scheduled sessions (i.e., therapist-led vs. parent-led sessions) in order to be more focused on their child; and 2) preference to have parent-led and/or child-initiated AME play between scheduled sessions. Parent interview data also supported child engagement, family normalcy, and parent self-efficacy as important potential mediators of intervention effects. Based on these studies, our team has established the AME as beneficial in managing child distress, and we have created a theoretically sound conceptual framework proposing mechanisms of action responsible for change in our targeted outcomes.

These studies have positioned our team well for the current study, which will now test the mechanisms of action (proximal/distal mediators; moderators) proposed in our conceptual framework. We know from our prior studies that the proposed study design/procedures are feasible and acceptable, that the AME is theoretically aligned with the guiding conceptual framework, [name]'s CSM-MT, and have preliminary effect size data about the relationship of the AME to our proposed proximal/distal mediators and outcomes.

## **2.0. OBJECTIVES AND SPECIFIC AIMS**

The objectives of this two group randomized controlled trial is to identify behavioral, sociological, and psychological variables contributing to positive outcomes observed in previous AME studies (i.e., mediators) and identify for whom the intervention works (i.e., moderators). We will examine proximal mediators of child engagement and parent-child interaction and distal mediators of perceived family normalcy, parent confidence (self-efficacy) about their ability to support their child during treatment, and independent parent/child use of music play to manage distress during hospitalization. We hypothesize that these factors mediate change in outcomes of child emotional distress, physical symptom distress, and quality of life; parent emotional/traumatic distress and quality of life; and family function. Published literature and our parent interview data support the proposed mechanisms of action; therefore, a mechanistic study of mediators and moderators of intervention effects is the next logical step. In some instances we will consent the child's caregiver if they are currently fulfilling the role of the parent. Specific aims and hypotheses are to:

### **Aim 1: Examine the effects of proximal and distal mediators of the Active Music Engagement (AME) intervention on outcomes for young children with cancer and parents.**

Hypothesis 1.1: Child engagement and parent-child interaction (proximal mediators) will mediate the effect of AME on perceived family normalcy, parent self-efficacy, and independent parent/child use of music play.

Hypothesis 1.2: Perceived family normalcy, parent self-efficacy, and independent parent/child use of music play (distal mediators) will mediate the effect of AME on child outcomes (emotional distress, quality of life), parent outcomes (emotional distress, traumatic distress, quality of life), and family function immediately post-intervention (Time 2) and 30 days post-intervention (Time 3).

### **Aim 2: Examine moderators of the AME intervention on outcomes for young child and parent distress.**

Hypothesis 2.1: Child and parent distress with prior hospitalizations and child age will moderate intervention effects for child emotional distress and parent emotional/traumatic distress outcomes at Time 2 and Time 3.

### **Aim 3 (Exploratory): Explore child physical symptom distress in mediation and moderation models.**

Hypothesis 3.1: Compared to attention control, children in the AME group will report less physical symptom distress (pain, fatigue, nausea) at Time 2 and Time 3.

Hypothesis 3.2: Perceived family normalcy, parent self-efficacy, and independent parent/child use of music play (distal mediators) will mediate the effect of AME on child physical symptom distress at Time 2 and Time 3.

**Hypothesis 3.3:** Child and parent distress with prior hospitalizations and child age will moderate intervention effects for child physical symptom distress at Time 2 and Time 3.

Findings will inform CSM-MT refinement and the use of music to manage treatment distress in other pediatric populations. Subsequent trials will examine AME cumulative effect across repeated admissions to manage distress and prevent traumatic stress symptoms in survivorship.

### **3.0. SAMPLE ELIGIBILITY CRITERIA**

**Child/Parent Inclusion Criteria and Rationale:** Children and parents/caregivers will be eligible if: 1) the child is 3 – 8 years of age at time of enrollment (intervention content is not age-appropriate for other children); 2) patients with an expected treatment course of at least 3 days to receive moderate to high intensity chemotherapy and/or radiation therapy either in-patient or outpatient (children receiving chemotherapy are at risk for high symptom distress; 3-day treatment course is required to deliver study conditions and contributes to sample homogeneity); and 3) one parent/caregiver ( $\geq 18$  years of age) can be present for all sessions (study targets both child and parent/caregiver).

**Child/Parent Exclusion Criteria and Rationale:** Children and parents/caregivers will be excluded if: 1) the child and/or parent/caregiver do not speak English or 2) the child has a significant cognitive impairment that might hinder participation (determination made in consultation with attending physician, oncologist, and parents).

**Sample Size.** We will recruit a total sample size of 184 child and parent/caregiver dyads (368 total) and assume 15% attrition in order to retain 156 child and parent/caregiver dyads (78 dyads/group) at Time 3.

### **4.0. PARTICIPANT RECRUITMENT AND ENROLLMENT**

Procedures mirror successful strategies used in Preliminary Study 3, and our current R01 music intervention study for adolescents/young adults undergoing high risk cancer treatment and their parent.

**Recruitment & Informed Consent.** The recruitment and informed consent procedures will preserve participants' right to refuse and guarantees that potential subjects who refuse will not be known to the research team. Children and parents/caregivers will be recruited from Riley Hospital for Children, Children's Mercy Hospital, Children's Healthcare of Atlanta, and University of Texas MD Anderson Cancer Center during clinic visits. As with our previous and current studies, the hematology/oncology coordinators, who will not be employed on the study, will identify potentially eligible parents/caregivers and children using an eligibility checklist. The coordinators then meet with potentially eligible parents/children to provide an initial study introduction, verify eligibility, and provide a study brochure. After the coordinators gain parent/patient approval, the coordinators will contact the project manager/PI to make contact with the parent/patient. The PI or project manager will contact the interested child/parent, explain the study, randomization procedures, intervention schedule, and assess willingness to participate. Written parent/caregiver consent for self and their child, and assent for children  $> 6$  years will be obtained, following the requirements of the human subjects review committee. The hematology/oncology coordinators are nurses who are trained and employed to enroll children/parents on clinical trials for their respective programs. We have worked closely with them on our previous and current studies with great success.

**Data Collection & Randomization Procedures.** Following consent, the project manager will arrange a time for parents/caregivers to complete baseline (T1) measures during a routine clinic visit, prior to their next scheduled chemotherapy admission. A trained evaluator will administer measures in a quiet/private setting and remain available for questions. The child/parent or caregiver dyad will then be stratified by child age (preschoolers 3-5 years; school-agers 6-8 years) and randomized in blocks of six to the AME or attention control condition by our statistician. After the PI or project manager from the enrolling site receives randomization status from our study statistician, she will inform the parent/child of their randomization status and will then immediately schedule Session 1. Only the

project manager, PI, statistician, and intervener will know the child/parent dyad's randomization status. Evaluators will be blinded.

[figure not shown]
All study condition sessions will be video recorded to facilitate collection of child engagement and parent-child interaction data and monitor treatment fidelity. Sessions 1 and 2 are video recorded to desensitize children/parents to video recording; only Session 3 video data are analyzed for Aim 1. In our previous studies, video recording did not negatively affect participant accrual. An evaluator, blind to randomization status, will administer T2 measures after Session 3. Evaluators will administer T3 measures 30 days (+/- 7 days) post-intervention during a subsequent clinic visit or by telephone. Parent self-reports will be used to monitor use of study condition activities between sessions and between T2 and T3 data collections (Appendix 1).

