All study condition sessions will be video recorded to facilitate collection of child engagement and parent-child interaction data and monitor treatment fidelity. Sessions 1 and 2 are video recorded to desensitize children/parents to video recording; only Session 3 video data are analyzed for Aim 1. In our previous studies, video recording did not negatively affect participant accrual. An evaluator, blind to randomization status, will administer T2 measures after Session 3. Evaluators will administer T3 measures 30 days (+/- 7 days) post-intervention during a subsequent clinic visit or by telephone. Parent self-reports will be used to monitor use of study condition activities between sessions and between T2 and T3 data collections (Appendix 1).

**Study Condition Procedures.** Consistent with our other studies, we train music therapists to deliver both intervention and control conditions to minimize risk for unblinding evaluators to participant group assignment. Risk for experimental drift, bias, and diffusion will be addressed through four quality assurance monitoring procedures established in our previous trials. Children/parents randomly assigned to AME or attention control receive the same length of sessions (45 min.) and timing of contact (3 sessions, 3 consecutive days). Session 1 will occur within 24 hours of hospital admission.

Usual care at all three sites. Across all sites, chemotherapy is administered according to Children's Oncology Group protocol guidelines, ensuring consistency of treatment. Antiemetic regimens are similar across sites and tailored to patient-specific needs. We will document patient medications at baseline, during hospitalization (T2), and 30 days post-intervention (T3) and control for site in all analytic models.

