Procedures. Following consent, the project manager will arrange a time for the parent to complete baseline measures during a routine clinic visit, prior to their next scheduled chemotherapy admission. Baseline measures will be completed in a private room in the outpatient clinic. A trained evaluator will administer the baseline measures and remain available for questions during measurement completion. The evaluator will immediately notify the project manager that baseline measures are completed. The child/parent dyad will then be randomly assigned to the AME or the attention control condition by the study statistician. The PI or project manager will then immediately notify the child/parent of their randomization status and schedule their first session with the intervener. Only the project manager, PI, statistician, and intervener will know the child/parent's randomization status.

AME Intervention. Parents/children randomly assigned to the AME intervention receive three, 45-minute sessions with the music therapist, delivered daily, for 3 consecutive days. Session 1 is delivered within 24 hours of hospital admission. AME intervention sessions are designed for delivery by a board-certified music therapist (MT-BC) who tailors music-based play experiences to encourage active engagement in and independent use of music play as a strategy to manage distress. During AME sessions, the music therapist provides children/parents repeated opportunities to experience competence, autonomy, and meaningful interactions through music-based play activities, and

provides support/education about ways music play can be used to manage distress and sustain a sense of family normalcy while hospitalized and as they transition home.

There are three components to the AME intervention: 1) therapist-led music-based play activities and sessions, 2) the music play resource kit (to promote independent music play), and 3) tip sheets for parent education and support that focus on why music play, how to use music play during hospitalization, and how to use music play during transition from hospital to home. During each session, the music therapist begins with a 5 minute introduction/assessment period, followed by a 30 minute music play session, and closes with a 10 minutes of parent education and tailored suggestions for using music play outside sessions.

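### Dyads are randomised and told their arm before the admission that triggers Session 1, so a course cancelled in between leaves a randomised dyad with no sessions, no Session 3 mediators and no defined T2 or T3 date

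*Combined protocol and SAP*

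**What the plan says.** Section 4.0 (Data Collection & Randomization Procedures) sets the order. After consent, parents "complete baseline (T1) measures during a routine clinic visit, prior to their next scheduled chemotherapy admission". Next, "The child/parent or caregiver dyad will then be stratified by child age (preschoolers 3-5 years; school-agers 6-8 years) and randomized in blocks of six". Once the enrolling site has the result, "she will inform the parent/child of their randomization status and will then immediately schedule Session 1". Section 5.0 repeats the order twice; its Procedures paragraph says "The PI or project manager will then immediately notify the child/parent of their randomization status and schedule their first session with the intervener".

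The start of treatment hangs on a later event. In Section 5.0 (Study Condition Procedures), "Session 1 will occur within 24 hours of hospital admission", and sessions run on three consecutive days. Section 3.0 requires an "expected treatment course of at least 3 days to receive moderate to high intensity chemotherapy and/or radiation therapy either in-patient or outpatient", so eligibility rests on an expectation held at enrolment.

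The measurements hang on the sessions. Child engagement and parent-child interaction are coded from the Session 3 video only. T2 follows Session 3, and T3 falls 30 days (plus or minus 7) after the intervention. In the Section 6.0 table, independent music play is reported at Sessions 2 and 3 and at T2.

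The plan does provide for incomplete dyads in general. Section 3.0 allows 15% attrition. Section 7.0 analyses as randomised, tries to obtain outcomes from non-completers, and uses maximum likelihood under missing at random with a pattern-mixture fallback.

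**The concern.** Allocation is fixed and disclosed while delivery still depends on an admission that has not happened. In the text I find no limit on the interval between randomisation and admission, no re-check of the expected course at admission, and no rule for a changed or cancelled admission. (The Study Schema figure is not reproduced in the text I worked from.)

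A dyad lost in that gap belongs to the randomised set but cannot contribute what Aim 1 needs. Section 7.0 asks for its outcomes, but the protocol gives no date on which to collect them. Its Session 3 behaviour did not go unrecorded; it never occurred. Mediation is the primary goal of Aim 1, so the gap touches the main analysis.

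Nor does early allocation seem to be needed. Section 5.0 states that "we train music therapists to deliver both intervention and control conditions", and session length and timing are the same in both arms, so Session 1 can be booked without knowing the arm.

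**Working it through.** **1. What each disruption does, given where Sections 4.0 and 5.0 anchor events**

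- *Postponed admission.* Session 1 is tied to the actual admission, so it moves, and Session 3, T2 and T3 move with it. The cost is an older T1 and a longer wait with the arm known.
- *Shortened stay.* One or two sessions may already have been given, and Section 5.0 (Setting) allows delivery in the outpatient clinic. Session 3 may still be lost, and with it the proximal mediators and the T2 anchor.
- *Cancelled course.* No sessions, no proximal mediators, and no defined T2 or T3 date.

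For a never-started dyad, three of the five Aim 1 mediators rely on sessions that did not take place: the two proximal ones, and independent music play as scheduled in Section 6.0. The other two, family normalcy and parent self-efficacy, are questionnaires that could be collected if T2 and T3 had dates.

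**2. The plan's own figure**

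Inputs from Section 3.0: 156 dyads retained (78 per group), 15% attrition.

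- 156 / (1 − 0.15) = 183.5, rounded up to 184. This reproduces the stated figure.
- Allowance: 184 − 156 = 28 dyads for all losses. The documents do not say whether losses before Session 1 are counted.

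**3. Size under an assumed non-start rate q**

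The documents give no q; 5% and 10% are illustrations. Cases A and B are alternatives, because a dyad's outcome is either observed or missing.

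*A. Outcomes collected and analysed as randomised.* Assume the same q in both arms and no intervention effect in non-starters. A simple between-arm effect is multiplied by (1 − q) and information by (1 − q)².

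- q = 5%: 0.95² = 0.9025, about 10% lost.
- q = 10%: 0.90² = 0.81, 19% lost.

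*B. Outcomes missing.* The loss is roughly q.

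- q = 5%: 184 × 0.05 = 9.2 dyads. q = 10%: 184 × 0.10 = 18.4 dyads.
- If these fall within the 15%, the 156 is kept, but about 9 or 18 of the 28 allowed losses are used before any session.
- If they come on top of the 15%: 184 × 0.95 × 0.85 = 148.6 and 184 × 0.90 × 0.85 = 140.8, so about 149 or 141 dyads remain. Keeping 156 would then need 156 / (0.85 × 0.95) = 193.2, so 194 dyads, or 156 / (0.85 × 0.90) = 203.9, so 204.

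None of these figures describes the percentile-bootstrap tests of indirect effects in Section 7.0. The plan states no alpha, power or effect size from which to work those out.

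**The case against.** The sponsor can fairly say that randomising after T1 already protects the baseline from knowledge of the arm, that Section 7.0 seeks outcomes from non-completers and has a missing-data plan, that T3 can be taken by telephone, and that the 15% allowance rests on prior studies. All of this stands, and it limits the harm. It does not supply a T2 or T3 date for a dyad without a Session 3. A telephone call still needs a date to be due.

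It is also fair that allocating after admission cannot stop a stay from being cut short later. Hence late allocation alone is not enough, and calendar dates for T2 and T3 are needed as well.

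Three stronger readings are tempting, and the documents do not support them:

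- *Every postponed, shortened or cancelled admission leaves no sessions and no anchor.* Only cancellation clearly does so (step 1 of the working).
- *Families told they drew storybooks will withdraw more.* This is possible but not documented. The attrition worry in Section 5.0 (Study Design) concerns usual care, and the same passage calls audio-storybooks acceptable.
- *Dilution and attrition add up.* They cannot both apply to the same dyad.

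**Conclusion.** The concern holds in a limited form. The documented order puts allocation and disclosure ahead of the event on which all delivery depends. A course cancelled in between leaves a randomised dyad with no exposure, no proximal mediators and no date for T2 or T3. The plan's general safeguards reduce this problem but do not remove it.

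The size is unknown. At assumed non-start rates of 5% to 10%, a simple between-arm comparison loses about 10% to 19% of its information if outcomes are collected, or roughly 5% to 10% if they are missing. In the second case the 28-dyad allowance may absorb the loss. The missing T2 and T3 dates and the absent mediators remain in either case and do not depend on q.

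The finding assumes that the Study Schema figure contains no interval limit or substitute dates. The change is cheap and worth making.

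**What to change.** 1. In Section 4.0 and Section 5.0 (both Data Collection & Randomization Procedures paragraphs, and Procedures), keep consent and T1 at the clinic visit and book Session 1 without reference to arm. Release the concealed allocation only once the child has been admitted, or has presented for outpatient treatment, and the expected course of at least 3 days has been re-confirmed, just before Session 1. A dyad whose course falls through earlier is then never randomised, and the as-randomised analysis is unaffected.
2. For randomised dyads who still do not reach Session 3, set calendar dates for T2 and T3, counted from randomisation or from the scheduled Session 1, identically in both arms. The outcome collection promised in Section 7.0 can then be carried out.
3. Reconcile the Session 1 timing, which is worded for hospital admission only, with the outpatient treatment and delivery allowed in Sections 3.0 and 5.0.

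The cost is protocol wording plus some logistics. The allocation must be released promptly within the 24-hour window, for example from a pre-generated concealed list in the REDCap system already in use, and both kits must be on hand at each site. Some dyads will complete consent and T1 without being randomised, so the 184 should count randomised dyads.

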**Study Design.** This is a two-group, randomized, controlled trial. Children and one parent will be stratified and randomized in blocks of six to the AME intervention or attention control condition (see Study Schema). Child/parent dyads will be stratified by child age (preschoolers 3-5 yrs; school-agers 6-8 yrs). Both conditions are standardized and each group will receive three 45-minute sessions over 3 days. We chose a randomized, controlled trial over a single-group trial as a control group is optimal for ruling out confounding variables that may impact the relationships between the intervention, mediators, and outcomes. For example, a single-group trial requires a dose be measured to represent the intervention since the variable being mediated must have some variation. The dose may be impacted by several unknown factors that could make interpretation of results difficult. Our prior studies suggest that 1) a usual care condition would likely have high attrition and negatively affect study accrual, and 2) our audio-storybooks low dose condition was acceptable without behavioral benefits. Thus, we will use audio-storybooks as our attention control condition. The number of sessions and amount of contact time were selected based on average length of stay and findings from our preliminary studies which found immediate and longer-term (30 days post-intervention) benefit.

As in our preliminary studies, baseline data (Time 1) will be intervention intervention collected after consent. Time 2 data are collected post-Session 3. Parents/children are encouraged to use AME and low dose audio-storybooks activities between sessions and at home following discharge and self-reported frequency and duration of activities will be collected during sessions 2 and 3, and at T3 (30 days post-intervention). Data collection timelines are based on positive findings from our preliminary studies and inform our primary aims which examine mediation. Findings will inform a subsequent trial to examine long term benefits. See Study Schema for assessment timelines.

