**Setting.** Young children (ages 3-8 years) and their parents will be recruited from three children's hospitals. These hospitals are in metropolitan areas that serve large catchment areas. All three sites are members of the Children's Oncology Group, which treats similar types of cancer diagnoses with similar therapeutic protocols. The inpatient hospital setting and outpatient hematology/oncology clinic will be used for delivery of intervention and attention control conditions; data collection will occur both in the clinic and in-patient setting. All sites have verified availability of dedicated, private space for these activities.

**Study Procedures.** Procedures mirror successful strategies used in Preliminary Study 3, and our current R01 music intervention study for adolescents/young adults undergoing high risk cancer treatment and their parent.

**Recruitment & Consent.** Children/parents will be recruited during a clinic visit. As with our previous/current studies, certified research coordinators will use the eligibility checklist to identify potential participants and notify the project manager. The project manager will then contact the child/parent, explain the study, and if they are interested, obtain written parent consent for themselves and their child and assent for children > 6 years, following human subjects review committee requirements.

**Data Collection & Randomization Procedures.** Following consent, the project manager will arrange a time for parents to complete baseline (T1) measures during a routine clinic visit, prior to their next scheduled chemotherapy admission. A trained evaluator will administer measures in a quiet/private setting and remain available for questions. The child/parent dyad will then be stratified by child age (preschoolers 3-5 years; school-agers 6-8 years) and randomized in blocks of six to the AME or attention control condition by our statistician. The PI or project manager will then immediately schedule Session 1. Only the project manager, PI, statistician, and intervener will know the child/parent dyad's randomization status. Evaluators will be blinded.

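### A single printed block size of six lets anyone who sees a whole age stratum deduce some upcoming assignments; varying, undisclosed block sizes would remove most of that certainty.

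*Combined protocol and SAP*

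**What the plan says.** Section 4.0 (Data Collection & Randomization Procedures) has dyads "randomized in blocks of six to the AME or attention control condition by our statistician". The Study Design paragraph of section 5.0 repeats it: "Children and one parent will be stratified and randomized in blocks of six to the AME intervention or attention control condition". The Data Collection & Randomization Procedures paragraph of section 5.0 gives the same size again. Child age is the only stratification factor named, with two levels. No passage varies the block size or withholds it from recruiting staff.

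On roles, section 4.0 (Recruitment & Informed Consent) says: "The PI or project manager will contact the interested child/parent, explain the study, randomization procedures, intervention schedule, and assess willingness to participate". Section 5.0 (Recruitment & Consent) says: "The project manager will then contact the child/parent, explain the study, and if they are interested, obtain written parent consent". The project manager then arranges the T1 visit, and the statistician randomizes once T1 is complete. Under section 4.0 the result goes to the PI or project manager of the enrolling site, who tells the family and schedules Session 1. On knowledge of the assignment, section 5.0 says: "Only the project manager, PI, statistician, and intervener will know". Evaluators are blinded.

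Section 4.0 also places an earlier step outside the study team. Hematology/oncology coordinators who are not employed on the study screen with a checklist, introduce the study and obtain the family's agreement before the PI or project manager is brought in. They are not among those listed as knowing allocations.

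**The concern.** Central assignment by the statistician after consent and T1 stops anyone from reading the next assignment. It does not stop someone from working it out. In a block of six with three places per arm, once one arm has used its three places the rest of the block is fixed. A person who knows the block size and the earlier assignments can then know the next arm. If that person also conducts consent conversations or sets the date of T1, the knowledge could affect how warmly the study is presented or when a dyad enters the list.

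What is at stake is selection of more motivated families into one arm. It would be hard to detect here. Parents are told their arm and complete every outcome measure in the section 6.0 table. Both primary outcomes named in section 7.0 (CHQ and POMS) are parent-reported. The CHQ is scheduled only at T2 and T3, so for the primary child outcome there is no baseline on the same scale that could reveal such selection.

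**Working it through.** **Inputs.** Block size 6 (sections 4.0 and 5.0). Two age strata (section 5.0). 184 dyads recruited, with the aim to "retain 156 child and parent/caregiver dyads (78 dyads/group) at Time 3" (section 3.0). The allocation ratio is not stated; 1:1, so 3+3 per block, is inferred from the equal group sizes. There are three sites (section 5.0, Setting) or four (section 4.0), so both are shown.

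**The plan's own figure.** 156 / (1 − 0.15) = 183.5, rounded up to 184, as stated. The plan gives no figure for predictability.

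**Step 1. Full sight, no intervening dyad.** There are 20 equally likely orderings of a 3+3 block. One arm has used all its places after 3 assignments with probability 2/20 = 0.1, after 4 with probability 0.4, and after 5 with probability 1.
- Certain assignments per block: 0.1 + 0.4 + 1 = 1.5 of 6, or **25%**.
- Best guess (the arm that is behind), by position 1 to 6: 0.5, 0.6, 0.6, 0.7, 0.7, 1.0. The sum is 4.1, and 4.1/6 = 41/60 = **68.3%**, against 50% by chance.
- In 184 dyads: 0.25 × 184 = 46. Simulation that allows for incomplete final blocks gives about 45, whether the strata split 92/92, 110/74 or 60/124.

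**Step 2. Lag between the judgement and the allocation.** List position is fixed when T1 is complete, not at consent, so other dyads in the stratum may be randomized in between. The number is not in the documents and is an assumption here. With k intervening dyads, the observer knows k fewer assignments of the block.

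| Intervening dyads | Certain | Best guess |
|---|---|---|
| 0 | 1.5/6 = 25% | 4.1/6 = 68% |
| 1 | (0.1 + 0.4)/6 = 8.3% | 3.6/6 = 60% |
| 2 | 0.1/6 = 1.7% | 3.4/6 = 57% |
| 3 | 0 | 3.2/6 = 53% |

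**Step 3. Sight of one site only, common list.** Assume equal sites and an observer who knows the position in the block. An assignment is certain only if all three exhausted places went to the observer's own site, which has probability (1/sites)³.
- Three sites: 0.25/27 = 0.9%, about 1.7 of 184.
- Four sites: 0.25/64 = 0.4%, about 0.7 of 184.

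If each site had its own list, site staff would be back near the 25% of step 1, less incomplete blocks.

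**Step 4. Varying block sizes.** Simulation with 92 dyads per stratum, full sight, no lag, and an observer who knows which sizes are possible but not the block boundaries. The size mixes are illustrative.

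| Sizes | Certain | Best guess |
|---|---|---|
| 6 only | 24% | 68% |
| 4 and 6 | about 5.5% | 69% |
| 4, 6 and 8 | about 2% | 68% |

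Varying the size removes most of the certain assignments. It does not lower best-guess accuracy.

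**The case against.** The safeguards in place are substantial. Assignment is central, follows consent and T1, and uses only two strata. Coordinators outside the study identify and first approach families. The lag in step 2 erodes certainty quickly, and staff who see one site's share of a common list can deduce almost nothing. The fix leaves the best guess where it was, and no bias has been shown. All of this stands, and it is why the point is minor. None of it closes the gap for someone who does see a full stratum and can influence consent or the timing of T1.

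Three stronger readings are tempting, and the documents do not support them.
- A reader might infer that the PI or project manager could choose whom to approach. Section 4.0 gives that step to the coordinators.
- A reader might take 25% and 68% as the expected rates. They are the ceiling under full sight and no lag.
- A reader might infer that the lead team has full sight because it monitors sessions at all sites. Section 5.0 (Protection Against Risk) describes review by the PI or co-investigator of random 25% samples of recordings, and section 4.0 sends each assignment to staff of the enrolling site. Sight across sites is possible, but nothing shows that anyone who consents families sees the whole ordered sequence.

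**Conclusion.** The concern holds as an avoidable weakness in allocation concealment, not as evidence of selection bias. The ceiling is 25% of assignments certain (about 45 of 184) and a 68% best guess. It rests on a 1:1 ratio, full sight of an age stratum and no intervening dyad. One intervening dyad reduces certainty to 8.3% and two reduce it to 1.7%; sight of one site's share of a common list leaves under 1%. Where the trial lies in that range cannot be settled, because the documents do not say whether lists are per site or who sees all sites. The exposure is limited to the consent conversation and the timing of consent and T1. This is a low-priority improvement.

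**What to change.** For any allocations still to be made (the documents do not state recruitment status), have the statistician generate randomly varying block sizes within each age stratum and hold the sizes in a restricted document. In all three places where the block size is printed (section 4.0, and the Study Design and Data Collection & Randomization Procedures paragraphs of section 5.0), replace it with a statement that permuted blocks of varying, undisclosed size are used. It would also help to state whether the list is common to all sites and who sees allocations across sites.

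The cost is a regenerated list for the remaining dyads and the wording changes. The sample size of 184, the age strata, the visits and the analysis stay as they are, and balance between arms is not noticeably affected.
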